#### **Endpoints:**

##### **Primary:**

Vascular function

Microbiome

##### **Secondary:**

Blood pressure

Whole blood epigenome

Whole blood and urine transcriptome

### **9.2 SAMPLE SIZE DETERMINATION**

Data will be tested for normality using the Shapiro-Wilk test. Continuous variables will be described as mean  $\pm$  standard deviation (SD) if normally distributed. Variables with skewed distribution (i.e. aldosterone, BNP, etc.) were logarithmically transformed prior to analyses and are presented as median and interquartile range (IQR). Categorical variables will be expressed as numbers (percentages).

When data are normally distributed, comparisons between the treatment (sodium intake) and control (placebo) groups will be made using paired Student's t-tests, and when data are non-

[figure not shown]
normally distributed, the Mann-Whitney U test will be employed. Chi-square test will be used for categorical variables. Tests for sodium intake effect on the primary outcomes without correction for period effect will be done using Mann-Whitney test on the differences. Tests for period effect will be assessed using two-sample Wilcoxon tests on the differences between treatment groups, and tests for carry-over effect will be assessed by a two-sample Mann-Whitney test on the averages in the two treatment periods. Correlations were determined with Pearson's correlation coefficient.

Additionally, we will evaluate the effects of sodium intake on changes in blood pressure, 24-hr ambulatory blood pressure monitoring (ABPM), biochemical markers, vascular functions, and specific transcriptome and epigenome by using a linear mixed model, with subject as a random effect, thereby accounting for the period, sequence, and carryover effects and to model the various sources of intra-individual and inter-individual variability. All statistical tests will be two-sided and P values  $<0.05$  will be regarded as significant. Statistical analyses will be carried out using SAS software (SAS Institute, Inc., Cary, NC, USA).

**Sample size and statistical power:** We expect to enroll and randomize a total of 40 eligible subjects for this protocol. The sample size is assessed to detect meaningful effects of sodium intake on the study's primary outcomes and secondary outcomes, including changes in vascular function (PWV m/s), sitting SBP and DBP (mm Hg), ABPM (mm Hg), biochemical markers (plasma aldosterone, pg/mL, brain natriuretic peptide (pg/mL), as well as epigenome, transcriptome, and microbiome under an assumption about the effect size, standard deviation outcomes, correlation of measurements within individual. We estimated that a sample size of 28 participants will be required in a cross-over study to detect changes in PWV between high salt intake and control groups of 0.6 m/s (estimates based on [Pimenta et al.](#) ), with 80% power and  $P < 0.05$ , assuming common SD of 0.9 m/s for high sodium intake and control groups, and correlation of 0.3 within subjects (Figure 2). Accounting for a potential of 20% dropout during the study, the sample size would be 34.

In addition, the estimated sample size will provide us with more than 80 percent power to detect a difference of 6 mm Hg (SD=9 mm Hg) in sitting SBP between sodium intake and the placebo treatment at 0.05 significance level (estimates based on [Tzemos et al.](#) ). Similarly, the proposed sample size would give more than 90% power to detect significant changes in plasma aldosterone (pg/ml) and brain natriuretic peptide (pg/mL) between high sodium intake and control at 0.05 significance level . The sample size calculation was performed using a paired *t* test assuming no carryover effect and no interactions between subjects, treatments, and periods.

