## 4 STUDY DESIGN

### 4.1 OVERALL DESIGN

This study involves a call-back and recruitment of 40 normotensive participants from the GENE-FORECAST protocol. Those in the upper tertile of vascular stiffness (as assessed by pulse wave velocity measures) will be oversampled. Participants will be randomized to a placebo or salt treatment arm for two weeks (Period 1), followed by a wash-out period for three-weeks, ending with a cross-over to the alternative treatment arm for two weeks (Period 2). The total length of participation is 7 weeks (Figure 1).

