#### 9.4.2 Analysis of the Primary Endpoints

The two primary endpoints are vascular function and microbiome.

First, vascular function difference between placebo and treatment (salt intake) will be estimated. Then, microbiome differential between treatment and placebo will be identified and estimate for each of the microbiome collection sides (skin, oral and gut). Details of the vascular function and microbiome analyses with respect to treatment and placebo are provided below.

Vascular function (e.g. pulse wave velocity, PWV) will be first analyzed as a continuous variable. Its relationship with salt intake will be investigated through multiple linear regression with vascular function as outcome and salt intake (a binary variable with two categories:

treatment and placebo) as exposure variable. For this analysis only samples with complete data for vascular function and salt intake will be considered. The outcome variable will be log transformed if it departs markedly from the Gaussian distribution. The aim of this first analysis is to estimate the effect of salt intake on vascular function. The effect size, p-value and 95% confidence interval will be provided as results.

The second endpoint is microbiome; the microbiome data of each of the all the collection sites (oral, gut and skins) will be analyzed separately. Prior to investigating the relationship between microbiome and salt intake, the raw microbiome data requires extensive processing and quality controls (QC) because of challenges posed by this type of data and the potential of spurious results if appropriate QC are not applied. The raw data will be processed in mainly 5 steps: (a) reads preparation (assembly of paired reads, filtering of low quality reads and identification of unique sequences), (b) Operational Taxonomic Units - OTU clustering (selection of unique OTU sequences), (c) quality controls (identification and removal of artifacts from amplicon reads, in OUT sequences). These tasks will be carried out using pipelines included in the standards operating protocols (SOPs) developed and used by the NIH Human Microbiome Project. For the metagenomic microbiome data, the *HUMANN2* pipeline will be used and for the 16s microbiome data the *DADA2* pipeline will be used.

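### In a cross-over trial sized on a paired t-test, section 9.2 falls back on the unpaired Mann-Whitney U test whenever the data fail a normality test

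*Combined protocol and SAP*

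**What the plan says.** Section 9.2 begins its analysis text with "Data will be tested for normality using the Shapiro-Wilk test". It does not say whether this means the raw values under each condition or the within-person differences. If the data are normal, "comparisons between the treatment (sodium intake) and control (placebo) groups will be made using paired Student's t-tests". If they are non-"normally distributed, the Mann-Whitney U test will be employed". The Wilcoxon signed-rank test, which is the paired rank test, is named nowhere.

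The same section contains three further provisions:

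- For the primary outcomes: "Tests for sodium intake effect on the primary outcomes without correction for period effect will be done using Mann-Whitney test on the differences".
- As an additional analysis, effects on blood pressure, ambulatory pressure, biochemical markers, vascular function and selected omics measures are to be evaluated "by using a linear mixed model, with subject as a random effect", allowing for period, sequence and carryover.
- Skewed variables, with aldosterone and BNP as examples, are to be log-transformed before analysis.

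On sizing, section 9.2 states "The sample size calculation was performed using a paired" t-test. The inputs are 28 participants, a PWV difference of 0.6 m/s, SD 0.9 m/s, within-subject correlation 0.3, 80% power and a 0.05 significance level.

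Section 9.4.2 analyses vascular function by multiple linear regression, with no subject term stated, and adds: "The outcome variable will be log transformed if it departs markedly from the Gaussian distribution". Section 9 says there will be no formal SAP, and no section says which of these analyses decides.

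**The concern.** Section 4.2 justifies the cross-over on the ground that each participant is their own control, and the sample size depends on that. The paired t-test respects it and the Mann-Whitney U test does not. When two measurements on one person are positively correlated, an independent-samples test uses too large a standard error, so its p-values are too large. The normality check therefore does more than choose between a parametric and a rank method: it also decides, from the trial's own outcome data, whether the pairing is kept.

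The check may also look at the wrong quantity. A paired t-test needs roughly normal within-person differences. Stable differences between people cancel out of those, but they remain in the raw values.

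**Working it through.** **Inputs.** From section 9.2: effect d = 0.6 m/s, SD s = 0.9 m/s, correlation r = 0.3, n = 28, two-sided 0.05. Assumed, because the documents do not give them: other correlations, and the shape of any skew.

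**1. The plan's own figure.** SD of the paired difference = s × √(2(1 − r)) = 0.9 × √1.4 = 1.065. The normal approximation gives n = ((1.960 + 0.842) × 1.065 / 0.6)² = 24.7, so 25. The noncentral t gives n = 27 (power 0.805), and n = 28 gives 0.820. The stated 28 is reproduced, and it depends on the pairing.

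**2. Effect of ignoring the pairing, by approximation.**
- Standard error used by an unpaired comparison: 0.9 × √(2/28) = 0.2405.
- True standard error: 1.065 / √28 = 0.2012.
- Ratio: 1/√(1 − r) = 1.195.
- True type I error: 2Φ(−1.960 × 1.195) = 2Φ(−2.343) = 0.019.
- Power of the unpaired comparison of means: Φ((0.6 − 1.960 × 0.2405) / 0.2012) = Φ(0.64) = 0.74, before any loss from using ranks.

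**3. Simulation of the tests themselves** (20,000 trials per setting, r = 0.3, effect 0.6 m/s):

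| n | Outcome shape | Paired t, power | Signed-rank, power | Mann-Whitney U, power | Mann-Whitney U, type I error |
|---|---|---|---|---|---|
| 28 | normal | 82% | 80% | 69% | 0.0205 |
| 34 | normal | 89% | 87% | 79% | 0.0223 |
| 40 | normal | 94% | 92% | 86% | 0.0222 |
| 28 | log-normal, log-SD 0.6 (assumed) | 82% | 90% | 92% | 0.0164 |

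At n = 28 with normal data, the type I errors of the paired t and signed-rank tests are 0.0497 and 0.0471. For Mann-Whitney U, type I error falls further as the assumed correlation rises: 0.007 at 0.5, 0.002 to 0.005 at 0.6, and 0.001 at 0.7.

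**4. The whole two-branch rule.** Suppose the check is run on each condition's raw values with normal within-person errors, n = 28 and r = 0.3. It then fires in about 10% of trials if the spread between people is normal, and in 18–19% if that spread is log-normal (assumed). Applied to the differences, it fires in about 5%. Overall power of the rule is 81% and 80% respectively, a loss of 1 to 2 points from 82%. As a rough check, 0.10 × (82 − 69) = 1.3 points. At an assumed r = 0.6 the loss is 2 to 6 points, but overall power is 90–94%.

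**The case against.** The best reply is that the fallback is one line among several.

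- Section 9.2 also provides a Mann-Whitney test on the differences for the primary outcomes and a mixed model with a subject effect. Both can keep the pairing. This stands, and it means that pairing is not lost throughout the plan. But neither is said to replace the fallback, and the model is described only as additional. The test on differences is also ambiguous. At n = 28 and r = 0.3 with normal data, comparing period differences between the two sequences keeps about 80% power; comparing salt-minus-placebo differences between sequences has about 5% power for the salt effect.
- PWV is not clearly bound for Mann-Whitney, because section 9.4.2 sends markedly non-Gaussian vascular function to a log transform. Aldosterone and BNP are also to be logged and may return to the paired t-test. This stands too, although section 9.4.2 sets no threshold for a marked departure.
- A conservative test creates no false positives, and Mann-Whitney U does not always lose power. With strong assumed skew at r = 0.3 it had 92% against 82% for the paired t-test. This is correct. Its type I error there was still under 2%, and the signed-rank test reached 90% with type I error of 0.044.

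A reader might also infer that recruitment makes the normality check fail often for PWV, since section 4.1 says "Those in the upper tertile of vascular stiffness (as assessed by pulse wave velocity measures) will be oversampled". The documents give no oversampling fraction and no PWV distribution, and they do not say that raw values are what is tested. That inference is conjecture.

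**Conclusion.** The point holds as an internal contradiction: the design and the sizing are paired, and the stated fallback is not. At n = 28 and r = 0.3 the fallback's nominal 5% test is really a test at about 2%, and below 1% at an assumed r = 0.6. With normal data at r = 0.3 it has about 69% power, against 82% for the paired t-test and 80% for a paired rank test.

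A reader might go further and conclude that the trial falls below its stated 80% power. The documents do not support that. At the plan's own correlation the complete rule still gives about 80–81%, power in the fallback branch can rise under strong skew, and other listed analyses can keep the pairing. The size of the problem is lost pairing and miscalibrated p-values wherever the fallback is used, together with a choice of test that depends on the outcome data. The correlations other than 0.3, the log-normal shapes and the frequencies with which the check fires rest on assumptions and not on figures in the plan.

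**What to change.** In section 9.2:

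1. Delete the Shapiro-Wilk switch and the Mann-Whitney U fallback for salt–placebo comparisons.
2. Make the mixed model already in the plan (subject random, with period and sequence terms) the primary analysis of the continuous outcomes, and align the regression text in sections 9.4.2 and 9.4.3 with it.
3. Judge normality only on within-person differences or model residuals.
4. Add the Wilcoxon signed-rank test with a Hodges-Lehmann interval as a fixed sensitivity analysis, reported whatever the data look like.
5. List in advance the outcomes to be log-transformed; aldosterone and BNP are already named. Whether PWV is transformed is the sponsor's choice, provided it is fixed before unblinding.

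The cost is a change of wording. It needs no further participants, visits or assays, and at n = 28 the signed-rank test still has about 80% power on the plan's inputs.

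### Section 9.2 names the same rank-sum test on undefined differences for both the salt and the period effect, and falls back to an unpaired test for paired data

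*Combined protocol and SAP*

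**What the plan says.** The design is a two-period cross-over. Section 4.1: "Participants will be randomized to a placebo or salt treatment arm for two weeks (Period 1), followed by a wash-out period for three-weeks", and then the alternative treatment.

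Section 9.2 lists these tests:

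- Normal data: "comparisons between the treatment (sodium intake) and control (placebo) groups will be made using paired Student's t-tests".
- Non-normal data: "the Mann-Whitney U test will be employed".
- Salt effect on the primary outcomes: "Tests for sodium intake effect on the primary outcomes without correction for period effect will be done using Mann-Whitney test on the differences".
- Period effect: "Tests for period effect will be assessed using two-sample Wilcoxon tests on the differences between treatment groups".
- Carry-over: "tests for carry-over effect will be assessed by a two-sample Mann-Whitney test on the averages in the two treatment periods".

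The same section adds an analysis of vascular function, blood pressure, biochemical markers and selected omics "by using a linear mixed model, with subject as a random effect, thereby accounting for the period, sequence, and carryover effects". Microbiome is not in that list. Section 9.4.2 gives a further analysis of vascular function: "Its relationship with salt intake will be investigated through multiple linear regression with vascular function as outcome and salt intake". It names no participant, period or sequence term. For microbiome, 9.4.2 gives per-feature negative binomial models.

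No one-sample or signed-rank test is named anywhere. The opening of section 9 says that there will be no formal SAP.

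**The concern.** Mann-Whitney and the two-sample Wilcoxon are two names for one rank-sum test. A plan that assigns it to differences for the salt effect, and again to differences for the period effect, has to say which differences and which two groups are meant in each case. In a two-period cross-over that choice decides whether the test responds to treatment or to period. Section 9.2 leaves it open.

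An analyst who took salt-minus-placebo differences and compared the sequences would in fact be testing period. A real salt effect would be reported as absent, or a drift between periods would be reported as a salt effect.

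The fallback is a separate fault that needs no interpretation. Section 4.2 justifies the design by each participant acting as his or her own control, and the sample size rests on a paired t-test. For non-normal data the plan then discards the pairing.

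**Working it through.** **Inputs (section 9.2).** PWV difference 0.6 m/s, SD 0.9 m/s, within-person correlation 0.3, two-sided 0.05, n=28; planned enrolment 40. The section 12 addendum reports 28 participants enrolled. The documents give no sequence ratio, so 1:1 is assumed, with no carry-over. Period drifts are assumptions and are shown as a range.

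**The plan's own figure.** SD of the within-person difference = 0.9 × √(2 × (1 − 0.3)) = 1.065 m/s. The exact paired t-test has power 0.805 at n=27 and 0.820 at n=28. The stated 28 reproduces.

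**Algebra.** Let τ be the salt effect and π the mean of Period 1 minus the mean of Period 2.

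| Difference | Salt-first mean | Placebo-first mean | Gap between sequences |
|---|---|---|---|
| Salt minus placebo | τ + π | τ − π | 2π |
| Period 1 minus Period 2 | τ + π | −τ + π | 2τ |

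On salt-minus-placebo differences, a between-sequence test sees only π. On period differences it sees only τ, and π has been removed. It is then a period-corrected salt test, which the sentence says it is not.

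**Simulated rejection rates** (10,000 trials per setting; 4,000 for the signed-rank test).

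| Setting | Rank-sum between sequences, salt − placebo | Rank-sum between sequences, P1 − P2 | Signed-rank, salt − placebo | Unpaired Mann-Whitney, salt values v placebo values |
|---|---|---|---|---|
| n=28, no salt effect, no drift | 0.048 | 0.043 | 0.049 | 0.019 |
| n=28, salt 0.6 | 0.042 | 0.781 | 0.797 | 0.686 |
| n=28, salt 1.2 | 0.042 | 1.0 | 1.0 | 0.999 |
| n=28, drift 0.3, no salt effect | 0.261 | 0.045 | 0.043 | 0.020 |
| n=28, drift 0.6, no salt effect | 0.789 | 0.044 | 0.021 | 0.014 |
| n=40, salt 0.6 | 0.051 | 0.926 | 0.935 | 0.861 |
| n=40, drift 0.3, no salt effect | 0.402 | 0.051 | 0.042 | 0.019 |
| n=40, drift 0.6, no salt effect | 0.918 | 0.050 | 0.022 | 0.014 |

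In the first test column, doubling the salt effect or raising n to 40 leaves rejection at the alpha level, as the algebra requires.

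**A third reading.** Table 2 in section 1.3 schedules vascular function and microbiome at all four visits, so the differences could be post-minus-pre changes, with salt-period changes compared against placebo-period changes as if independent. Assuming the same correlation of 0.3 between all four visits (compound symmetry), each change has SD 1.065. The standard error of the comparison is 1.065 × √(2/28) = 0.285 m/s, against 1.065/√28 = 0.201 m/s for the paired comparison of end-of-period values. Simulated power for 0.6 m/s is about 51% at n=28 and 67% to 69% at n=40, with type I error about 5%.

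**The fallback.** With n=28 values per treatment treated as independent, the standard error used is in effect 0.9 × √(2/28) = 0.241, while the true one is 0.201. The working critical value is therefore 1.96 × 0.241/0.201 ≈ 2.35 instead of 1.96, a true two-sided level of about 2%. This agrees with the simulated 0.019. Power is 0.69 against 0.80 for the signed-rank test at n=28, and 0.86 against 0.94 at n=40.

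**The case against.** The strongest reply is that the damaging reading is only one of several. The differences are undefined. The change-score reading is a genuine salt test, uses two samples and does not correct for period, so it fits the sentence as labelled. The sentence may also contain a naming slip: the period and carry-over tests are each called two-sample, the salt test is not, and a misnamed signed-rank test would fit. This stands. The no-power result holds only for salt-minus-placebo differences compared between sequences.

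The second reply is that the salt conclusion does not hang on this sentence. The paired t-test, the mixed model for vascular function and the section 9.4.2 models all address salt. A reader might infer from the cancellation that the trial cannot detect a salt effect, that this is its only rank test for the primary outcomes, or that the sample size of 28 is wrong. The documents support none of these. The other analyses are written into the plan, the general non-normal fallback is also a rank test and retains 69% power, and 28 follows correctly from a paired t-test.

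Two things remain. The plan does not say which salt analysis decides, and no formal SAP is planned that would settle it. The unpaired fallback is a fault however the salt sentence is read.

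**Conclusion.** The point holds as a wording defect that can change a result; it should be fixed. One procedure is named for two different effects on differences that are never defined. What follows at n=28 depends on the reading:

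- Salt minus placebo, between sequences: a period test. Rejection is about 5% whatever salt does, and 26% to 79% for assumed drifts of 0.3 to 0.6 m/s without any salt effect.
- Period 1 minus Period 2, between sequences: a sound salt test with 78% power, but period-corrected, contrary to its label.
- Post-minus-pre changes compared as independent groups: valid but inefficient, at about 51% power.

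Independently of this, the fallback costs about 11 percentage points of power (80% to 69%) and runs at a true type I error near 2%.

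The cancellation is algebra and needs no assumption beyond the reading. The percentages rest on the plan's PWV inputs, normally distributed simulated data, 1:1 sequences, no carry-over, the assumed drifts and, for the change-score reading, compound symmetry over the visits.

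**What to change.** Reword section 9.2, defining the differences and the groups in each sentence:

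1. Salt effect without period correction: Wilcoxon signed-rank test on within-person salt-minus-placebo differences.
2. If a period-adjusted rank test is wanted: rank-sum comparison of the two sequences on Period 1 minus Period 2 differences, labelled as period-adjusted.
3. Period effect only: rank-sum comparison of the two sequences on salt-minus-placebo differences.
4. Non-normal fallback for the paired t-test: the signed-rank test in item 1 (or the test in item 2) in place of the unpaired Mann-Whitney.

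It would also help to state which salt analysis decides each primary endpoint, since sections 9.2 and 9.4.2 offer several.

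The cost is a few sentences in a protocol amendment. No new data, visits or participants are needed, and the sample size is unaffected.

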**Table 2: Specific activities by visit**

Activity	Visit 1 (baseline)	Visit 2 (after 2-week treatment)	Visit 3 (after 3-week washout)	Visit 4 (after second 2-week treatment)
24-Hour nutrient recall	x	x	x	x

Psychophysical Taste Task: Sucrose and Salt Detection Thresholds	x	x	x	x
Psychophysical Taste Task: Sucrose and Salt Preference	x	x	x	x
History and physical exam with medication history	x	x	x	x
Baeke's physical activity questionnaire	x			
Pittsburg sleep questionnaire	x			
Stool/skin/mouth swabs for microbiome analysis	x	x	x	x
Urine sample	x	x	x	x
Blood sample	x	x	x	x
Vascular function	x	x	x	x
24-hour blood pressure monitor given to participant	x		x	
24-hour blood pressure monitor returned by participant		x		x

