## **9 STATISTICAL CONSIDERATIONS**

The protocol will not have a formal Statistical Analytical Plan (SAP).

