### 9.4 STATISTICAL ANALYSES

#### 9.4.1 General Approach

For descriptive statistics, categorical variables will be assessed via chi-square and presented as percentages. Continuous variables will be assessed via t-test and will be presented as means with standard deviations. We will check assumptions underlying statistical procedure and correct procedure if necessary.

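### The additional mixed model is said to adjust for period, sequence and carryover; an explicit carryover term makes the salt effect inestimable or much less precise, so the terms and visits should be fixed

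*Combined protocol and SAP*

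**What the plan says.** Section 9.2 first gives paired t tests and rank tests. It then says that "we will evaluate the effects of sodium intake on changes in blood pressure", ambulatory pressure, biochemical markers, vascular function and selected transcriptome and epigenome measures in a linear mixed model with participant as a random effect, "thereby accounting for the period, sequence, and carryover effects". The microbiome is not in that list.

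The section gives no list of fixed effects and no coding for carryover. It does not say which visits supply responses, or which visit a change is measured from.

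Other places bear on the point:

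- Section 9.2 has a separate carryover check: "tests for carry-over effect will be assessed by a two-sample Mann-Whitney test on the averages in the two treatment periods".
- The sample size in Section 9.2 rests on a paired t test, "assuming no carryover effect and no interactions between subjects, treatments, and periods".
- Section 9.4.2 gives the main analysis of vascular function: "Its relationship with salt intake will be investigated through multiple linear regression with vascular function as outcome". It lists no period, sequence, carryover or participant term. Section 9.4.3 does the same for blood pressure.
- Section 1.3 ("Table 2: Specific activities by visit") schedules vascular function, blood and urine at all four visits. Visits 2 and 4 close the two treatment periods.
- Section 9 states: "The protocol will not have a formal Statistical Analytical Plan (SAP").

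**The concern.** A random participant effect handles correlation within a person. It does not adjust for period, sequence or carryover; each needs a fixed term. Taken at its word, the sentence therefore calls for salt plus three further effects. A two-sequence, two-period crossover with one outcome per period cannot support that, because sequence and carryover occupy the same between-sequence contrast.

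Software would usually drop one aliased column and still print a salt estimate, and that estimate depends on which column went. The versions that can be estimated with an explicit carryover term give up much of the precision for which the crossover was chosen. No later SAP is promised in which the choice would be settled.

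**Working it through.** **Inputs.** From Section 9.2: salt effect 0.6 m/s in pulse wave velocity, SD 0.9 m/s, within-participant correlation 0.3, two-sided 0.05, 28 participants required and 40 planned. Section 12 reports 28 enrolled. Assumed here: 1:1 allocation to sequences and, for the four-visit models only, correlation 0.3 between every pair of visits.

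**The plan's own figure.** SD of a paired difference = 0.9 × √(2 × (1 − 0.3)) = 1.065. By the noncentral t distribution, power is 80.5% at 27 and 82.0% at 28, so the stated 28 is reproduced within rounding.

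**Estimability with one outcome per period.** Let μ be the intercept, π period 2, σ the placebo-first sequence, τ salt, and λ carryover of salt into the following placebo period.

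| Sequence | Period 1 | Period 2 |
|---|---|---|
| Salt first | μ + τ | μ + π + λ |
| Placebo first | μ + σ | μ + π + σ + τ |

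There are four cell means and five parameters, and the matrix has rank 4. Adding k to τ, 2k to λ and k to σ, and taking k from μ and from π, leaves every cell unchanged. Salt is therefore not estimable. One change score per period gives the same matrix. What the four means do estimate is:

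- Within participants, averaged over sequences: τ − λ/2.
- Period 1 between groups: τ − σ.
- Difference between sequences in period averages: λ/2 − σ. This is the plan's carryover check, and it cannot separate λ from σ.

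**Sequence kept, no carryover term.** Salt is the within-participant contrast. SE = 1.065/√28 = 0.201, or 1.065/√40 = 0.168. Power (noncentral t, n − 2 df) is 82% at 28 and 93% at 40.

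**Carryover in place of sequence.** Four parameters fit four means exactly, so salt is the Period 1 comparison. SE = 0.9 × √(2/14) = 0.340, or 0.9 × √(2/20) = 0.285. Power is 40% at 28 and 54% at 40.

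**Same data, different answers.** Take 14 per sequence, true salt effect 0.6, no carryover, and an assumed chance sequence difference of 0.3 m/s. The SE of that difference is √(0.81 × 1.3/2 × 2/14) = 0.274, so 0.3 is about 1.1 SE.

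| Model | Salt estimate | SE | p (26 df) |
|---|---|---|---|
| Carryover dropped | 0.60 | 0.201 | 0.006 |
| Sequence dropped, placebo-first group 0.3 higher | 0.30 | 0.340 | 0.39 |
| Sequence dropped, placebo-first group 0.3 lower | 0.90 | 0.340 | 0.014 |

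The shift can go either way.

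**All four visits as responses.** With visit effects, salt and carryover, the model is of full rank with or without sequence. Power depends on how carryover is coded. The ranges cover n − 2 to 3(n − 2) df.

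| Carryover coding | Sequence kept, N=28 | Sequence dropped, N=28 |
|---|---|---|
| Visit 4 only | 38–40% | 45–47% |
| One effect common to Visits 3 and 4 | 53–55% | 63–65% |
| Separate effects at Visits 3 and 4 | 30–31% | 43–45% |

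With no carryover term the four-visit SE at 28 is 0.201, the same as from Visits 2 and 4 alone.

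**The case against.** The plan never says that separate sequence and carryover terms will be fitted to one outcome per period. Of the possible readings, only that one makes salt inestimable. One between-sequence term standing for both effects has no fault, and using all four visits keeps salt estimable. The separate carryover test and the no-carryover sample size suggest that the authors may not intend a carryover term in the salt model. The model is also introduced as an addition: the paired t test already uses each participant as their own control and, under equal allocation, a period effect does not bias it. The four-visit power figures rest on a correlation pattern that the documents do not give.

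Most of this stands, and it limits the point to one supplementary model. It does not remove it. The sentence claims a carryover adjustment, and every way of carrying that out with an explicit term, among those tried, gives either no salt estimate or one with at most 65% power at 28 participants.

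A reader might also infer that Section 9.4.1 ("We will check assumptions underlying statistical procedure and correct procedure if necessary") lets the team choose the carryover coding after seeing results. That sentence is about checking assumptions, and the documents do not support reading it as such a licence. The gap is simply that the terms are not stated.

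**Conclusion.** The point holds for the additional mixed model and should be fixed. With one outcome or change score per period, separate sequence and carryover terms leave salt inestimable; this is algebra and needs no assumption. Replacing sequence by carryover raises the standard error at 28 participants from 0.201 to 0.340 and cuts power from 82% to 40%, given the plan's inputs and 1:1 allocation. The four-visit range of 30–65% also needs equal correlation of 0.3 across visits.

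A reader might infer that the trial cannot estimate the salt effect, or that its main analyses fail for this reason. The documents do not support that. The paired t test and the regressions in Sections 9.4.2 and 9.4.3 carry no carryover term, the microbiome is outside this model, and dropping the carryover term restores a full-rank model.

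**What to change.** Replace the description of the mixed model in Section 9.2 with wording such as:

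> The mixed model has fixed effects for treatment, period and sequence and a random participant effect, with no carryover term. The comparison of period averages is a descriptive check for carryover and does not change the analysis.

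State which visits are responses: Visits 2 and 4, with Visits 1 and 3 as covariates if the sponsor wants them. Define what is meant by a change. Whichever visits are used, separate sequence and carryover terms should not be fitted to one outcome per period.

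The change needs no new data or visits. Under equal correlation 0.3, not using Visits 1 and 3 as responses costs no precision.

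The price is reliance on the three-week washout, which the sample size already accepts. An assumed residual of 0.3 m/s from salt in the following placebo period would bias the salt effect by −0.3/2 = −0.15 m/s.
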